### **9.3.2 Clinical Laboratory Assessments**

For the laboratory assessments during TE period, the observed values and change from baseline values of the continuous hematology, coagulation and chemistry results will be summarized in SI units at each visit. Change from baseline in coagulation will be summarized for subjects from parent study 445-117 only.

The number and percentage of subjects meeting at least 1 threshold analysis criterion event during the TE period will be summarized. The threshold analysis criterion shift from baseline will also be summarized for selected laboratory parameters. The threshold analysis criteria are provided in [Appendix E](#).

Results of urinalysis and positive urine/serum pregnancy test will be presented in individual subject data listings only. For positive serum pregnancy listing, subjects with serum HCG which are abnormally high will be selected.

In addition, a listing containing individual subject hematology, chemistry, and coagulation values will be provided. This listing will include data from both scheduled and unscheduled visits.

### **9.3.3        *Electrocardiogram***

For the following ECG interval measurements during the TE period, a summary of observed values and change from baseline values will be provided at each visit (in msec): RR, PR, QT, and QT corrected for HR (QTcF), QRS duration, and HR (beats per minute).

The number and percentage of subjects meeting at least 1 threshold analysis criterion event during the TE period will be summarized. The threshold analysis criteria are provided in [Appendix E](#).

### **9.3.4        *Vital Signs***

For the vital signs measurements during the TE period, the observed values and change from baseline values will be summarized at each visit. The following vital signs parameters will be summarized: BMI ( $\text{kg}/\text{m}^2$ ), weight (kg), systolic and diastolic blood pressure (mm Hg), body temperature ( $^{\circ}\text{C}$ ), pulse rate (beats per minute), and respiratory rate (breaths per minute).

The number and percentage of subjects meeting at least 1 threshold analysis criterion event during the TE period will be summarized. The threshold analysis criteria are provided in [Appendix E](#).

### **9.3.5        *Pulse Oximetry***

For the percent of oxygen saturation measurements using pulse oximetry during the TE period, a summary of observed values and change from baseline values will be provided at each visit.

The number and percentage of subjects with shift changes from baseline (normal/missing and low according to the reference range) to the lowest percent of oxygen saturation during the TE period will be summarized.

### **9.3.6        *Physical Examination***

No tables/figures/listings will be provided for physical examination data.

### **9.3.7        *Ophthalmology Examination***

Ophthalmology examination results will be provided in a data listing.

### **9.3.8        *COVID-19 Impacted Visits***

A listing containing subjects' visits impacted due to COVID-19 will be provided.

## **10            *Interim and DMC Analyses***

### **10.1        *Interim Analysis***

Not applicable.

**10.2 DMC analysis**

Not applicable.

## 12 APPENDICES

### Appendix A: Analysis Visit Windows for Safety Assessments

Table 12-1 Analysis Visit Windows Safety Assessments			
Assessment	Visit	Target Study Day	Analysis Visit Window (in study days)
Weight, Height and BMI	Baseline	--	defined in section 9.1
	OL Week 12	85	[1, 127] where Day 1 is post-dose measurement
	OL Week 24	169	(127, 211]
	OL Week 36	253	(211, 295]
	OL Week 48	337	(295, 351]
	OL Safety Follow-up	Not applicable	Use nominal visit
Vital Signs Hematology Serum Chemistry	Baseline	--	defined in section 9.1
	OL Week 12	85	[1, 127] where Day 1 is post-dose measurement
	OL Week 24	169	(127, 211]
	OL Week 36	253	(211, 295]
	OL Week 48	337	(295, 351]
	OL Safety Follow-up	Not applicable	Use nominal visit
Standard 12-lead ECG	Baseline	--	defined in section 9.1
	OL ETT or Departing	Not applicable	Use nominal visit (ETT or Departing Visit)
	OL Safety Follow-up	Not applicable	Use nominal visit
Coagulation 	Baseline	--	defined in section 9.1
	OL Week 24	169	[1, 253] where Day 1 is post-dose measurement
	OL Week 48	337	(253, 351]
	OL Safety Follow-up	Not applicable	Use nominal visit

Notes:

 Visit name for analysis purpose is used to report data in tables and figures.

 The analysis visit windows will be applied using the following rules for both scheduled and unscheduled visits:

1. If no numerical measurement is available within a visit window, the measurement will be considered missing for the visit.
2. If there is more than 1 numerical measurement available within a visit window, use the following rules:
  - i. The measurement closest to the target day will be used; or
  - ii. If there are multiple measurements with the same distance from the target day, the latest measurement will be used. If the latest measurement cannot be determined, then unscheduled visit will be selected.

 For measurement collected on the date of first dose of study drug in Treatment Period, if it cannot be determined whether the measurement is before or after the first dose:

1. Scheduled measurement will be treated as pre-dose observation.
2. Unscheduled measurement will be treated as post-dose observation.

 For safety assessments, Safety Follow-up analysis visit will be based on nominal Safety Follow-up visit. If a subject does not have a nominal Safety Follow-up visit but has an ETT visit with study day >351, then the ETT visit will be mapped into Safety Follow-up analysis visit for the corresponding part.

 Baseline coagulation applies to subjects from parent study 445-117 only; baseline coagulation will be missing for subjects from parent study 445-126.

Derived Variables for each part:

1. Age (in years) at first dose date and post-baseline visit (for demographics, listing and the calculation of [percent] predicted spirometry variables):

Obtain the age at informed consent in “yy, mm” format (e.g., 24 years, 6 months) from the Vital Signs (VS) page at the Day 1 Visit and add 0.5 month to convert to days.

Obtain the informed consent date.

Then age (in years) at first dose or post-baseline visit = [(first dose date or post-baseline visit date – informed consent date) in days + age at informed consent (in days)]/365.25.

2. Missing first dose date or last dose date

If the first dose date is missing, use Day 1 visit date.

If the last dose date of study drug is not available and there is no data to indicate that the subject discontinued treatment, the data cutoff date will be used instead.

If the subject discontinued treatment and the last dose date is missing or partial date is reported, the last dose date will be imputed based on, in descending order priority, the Early Treatment Termination (ETT) visit date, last visit date before the Safety Follow-up, or the last study drug administration date from EX SDTM domain, as appropriate. The imputation algorithm will ensure the imputed last dose date does not exceed the data cutoff date.

3. Electrocardiogram:

Baseline is defined in Section 8.1. If multiple ECG measurements are obtained on the same calendar day during the TE period,

- o For summary purpose, the average value will be used as the ECG on that day;
- o For threshold analysis purpose, all ECG values will be used

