| Height and weight              | X                                         |                                                          | X                                   | X                          | X                                             | X                                                                                       | Height and weight will be measured with shoes off (Section 11.2.4). For subjects whose date of informed consent occurs after their 21st birthday, height will not be collected in this study. For subjects whose date of informed consent occurs on or before their 21st birthday, height will be collected through the first visit after the subject's 21st birthday and does not need to be collected at future visits.                                   |
| Vital signs and pulse oximetry | X                                         |                                                          | X                                   | X                          | X                                             | X                                                                                       | Complete before other assessments after subject has rested for at least 5 minutes (Sections 11.2.3 and 11.2.5).                                                                                                                                                                                                                                                                                                                                             |
| Standard 12-lead ECG           | X                                         |                                                          |                                     | X                          | X                                             | X                                                                                       | Complete before other assessments after subject has rested for at least 5 minutes (Section 11.2.6)                                                                                                                                                                                                                                                                                                                                                          |

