### **9.1.2 Follow-up**

Subjects will have a Safety Follow-up Visit 28 ( $\pm$  7) days after the last dose of study drug. Safety Follow-up Visit assessments are listed in Table 3-1.

The Safety Follow-up Visit is required for all subjects. However, subjects who transition within 28 days of the last dose of study drug to either:

- a commercially available Vertex CFTR modulator regimen

- managed-access-program-supplied Vertex CFTR modulator regimen
- or, to another qualified Vertex study

will complete the Week 48 Visit (or the Early Termination of Treatment [ETT] Visit/Departing Visit, if the transition occurs before the Week 48 Visit). In these cases, the Week 48 Visit (or the ETT Visit/Departing Visit) will replace the Safety Follow-up Visit.

For subjects who complete an ETT Visit/Departing Visit 3 weeks or later following the last dose of study drug, the ETT Visit/Departing Visit will replace the Safety Follow-up Visit (Section 9.1.3).

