#### **12.3.4.3 Electrocardiogram**

For the TE ECG measurements, a summary of observed values and change from baseline values will be provided at each time point during the TE Period, for the following ECG interval measurements (in msec): RR, PR, QT, QT corrected for HR intervals (QTcF), QRS duration, and HR (beats per minute).

For threshold analysis, the number and percentage of subjects with at least 1 threshold event during the TE Period will be summarized. The threshold criteria will be provided in the SAP.

Additional ECG analyses may be described in the SAP.

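### SAP Table 12-1 has no Week 48 row for ECGs, so the promised by-visit ECG summary has no place for the only end-of-treatment ECG of subjects who complete without departing

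*SAP*

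**What the plan says.** Protocol Table 3-1 marks the standard 12-lead ECG (the row with the comment "Complete before other assessments after subject has rested for at least 5 minutes (Section 11.2.6") at Day 1/Returning, Week 48, ETT/Departing and Safety Follow-up. No ECG is scheduled from Week 4 to Week 44.

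Protocol 12.3.4.3 says that "a summary of observed values and change from baseline values will be provided at each time point during the TE Period". SAP 9.3.3 repeats the promise: "a summary of observed values and change from baseline values will be provided at each visit (in msec".

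SAP 9.1 sends the reader to Appendix A for the windows of protocol-defined visits. Footnote 1 of Table 12-1 gives the status of the names listed there: "Visit name for analysis purpose is used to report data in tables and figures". The ECG block lists three: Baseline, OL ETT or Departing ("Use nominal visit (ETT or Departing Visit"), and OL Safety Follow-up, also by nominal visit. One remapping rule exists, in footnote 4, and its condition is "If a subject does not have a nominal Safety Follow-up visit but has an ETT visit with study day >351".

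**The concern.** The SAP text promises a Week 48 ECG summary and the table that defines the reporting visits has no row for it. ECGs are a named part of the primary endpoint. Dosing runs to the evening before the Week 48 Visit, so for a subject who completes without departing, Week 48 is the only scheduled ECG at the end of treatment.

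An ETT Visit is held only when treatment stops early, so that row does not cover completers. Their only reported post-dose ECG would be the Safety Follow-up one, taken off drug. Some completers would not have even that. For those who move within 28 days of the last dose to a commercial or managed-access regimen, or to another qualified study, Protocol 9.1.2 states: "In these cases, the Week 48 Visit (or the ETT Visit/Departing Visit) will replace the Safety Follow-up Visit".

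The ECG block is also the only one with no study-day window after baseline. The SAP 9.1 rule that places unscheduled values in scheduled visit windows therefore has nothing to act on for ECGs.

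**Working it through.** **Reproducing the table's own figures.** Target day = 7 × week + 1, which gives 85, 169, 253 and 337 for Weeks 12, 24, 36 and 48. The boundaries are midpoints between neighbouring target days: (85 + 169)/2 = 127, (169 + 253)/2 = 211, (253 + 337)/2 = 295. For coagulation, (169 + 337)/2 = 253. The last upper limit is 337 + 14 = 351. All agree with Table 12-1. The protocol's Week 48 visit window, 337 ± 5, is days 332 to 342.

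**Study-day windows after baseline, by block.**

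| Block | Windows | Week 48 row |
|---|---|---|
| Weight, height, BMI | 4 | yes |
| Vital signs, hematology, chemistry | 4 | yes |
| Coagulation | 2 | yes |
| ECG | 0 | no |

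**Scheduled against reported.** ECGs scheduled in Protocol Table 3-1 after Day 1/Returning: {Week 48, ETT/Departing, Safety Follow-up}. ECG rows after baseline in Table 12-1: {ETT/Departing, Safety Follow-up}. The difference is {Week 48}. Footnote 4 moves only late ETT visits. Footnote 2 selects the value nearest a target day, and the ECG block has none.

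**Scheduled ECGs after the first dose in this study that have a row.**

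| Path | With a row |
|---|---|
| Completes, has Safety Follow-up | 1 of 2 |
| Completes, Week 48 replaces Safety Follow-up | 0 of 1 |
| ETT, then Safety Follow-up | 2 of 2 |
| Departs, does not return | 1 of 1 |

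A subject who departs, returns and completes keeps the Departing row but has no row for the Week 48 ECG.

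**What the Safety Follow-up row contains.** The visit is at 28 ± 7 days, that is 21 to 35 days after the last dose, 15 permitted days. The TE Period ends no later than 28 days after the last dose. Days 21 to 28 (8 days) can fall inside it; days 29 to 35 (7 days, 7/15 = 47%) fall outside. These are calendar days, not a forecast of subjects.

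**Numbers affected.** The documents give no completion rate. As an assumption only, if 0 to 30% of 160 subjects stopped early, 160 × 0.70 = 112 to 160 would reach Week 48 with an ECG that has no row.

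**Testing the obvious repair.** Copying (295, 351] into the ECG block would let an ETT/Departing ECG on any of 351 − 295 = 56 days (296 to 351) fit two rows, and would leave unscheduled ECGs up to day 295 unassigned. A nominal-visit row avoids the double placement.

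**The case against.** The best defence is that the literal reading is not forced. SAP 9.3.3 and Protocol 12.3.4.3 already require every visit; footnote 1 does not say that unlisted visits are excluded; and a scheduled Week 48 ECG carries its nominal label, so a programmer could simply use it. The table may also not be exhaustive: pulse oximetry has no named block, though SAP 9.3.5 promises it by visit. This shows that a sensible team might recover the row. It does not remove the inconsistency. An assessment with no block differs from a block that names its visits and leaves one out, and the table states the nominal-visit instruction wherever it intends it.

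On unscheduled ECGs, the same list in SAP 9.1 still uses them for baseline, last on-treatment, maximum and minimum values, and listings. That stands: only their place in the by-visit summary is undefined, and reporting sparse ECGs by nominal visit is a legitimate choice.

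The Safety Follow-up day count applies equally to other assessments and is not changed by the repair. That also stands; the count only describes what would be left in the ECG table. The path tally counts visits that have a row, not ECGs guaranteed to be taken, since Protocol 9.1.3 lets a same-day Departing Visit rely on the other study's assessments.

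The impact is narrow. The analysis is descriptive, and Appendix A says: "For threshold analysis purpose, all ECG values will be used". Protocol 12.3.4 lists all safety data by subject. This limits the weight of the point and is accepted.

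Loss of a row when the PDF was read cannot be fully excluded, but the other three blocks are intact and the ECG block reads as complete.

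**Conclusion.** The point holds. The SAP's text and its visit table disagree, and the table followed as written leaves the Week 48 ECG out of the by-visit summaries of RR, PR, QT, QTcF, QRS and HR. For completers who never departed, that leaves one off-drug value or none. The ceiling is the approximately 160 planned subjects; the actual number depends on a completion rate that the documents do not give. Threshold results and listings are unaffected. It should be fixed, because it concerns a component of the primary endpoint and the remedy is trivial. Confidence is high, on the assumption that the extracted table is complete.

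**What to change.** Before database lock, add one row to the Standard 12-lead ECG block of Table 12-1: `OL Week 48 | 337 | Use nominal visit`. The target-day cell could equally read as not applicable, as in the other nominal rows; the difference is cosmetic.

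Add one sentence saying where unscheduled and Returning Visit ECGs go, for example to the threshold analysis and listings only. If a day-based window is preferred, state that nominal ETT/Departing ECGs stay in their own row and are not also counted at Week 48, and say where ECGs before the lower limit fall.

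The cost is one row and one sentence, made as a SAP amendment if the plan is already approved. No new data are needed.

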b If the subject prematurely discontinues study drug treatment, an ETT Visit should be scheduled as soon as possible after the decision to discontinue treatment (Section 9.1.3). If the subject prematurely discontinues treatment to participate in another qualified Vertex study, the Departing Visit should be completed before or on the same day as the visit at which they receive the first dose of study drug in the Run-in Period of the other qualified Vertex study. The Safety Follow-up Visit will not be required if the subject enrolls in the other qualified Vertex study within 28 days of the last dose of study drug in this study.

c The Safety Follow-up Visit is required for all subjects, unless otherwise specified. For subjects who complete an ETT Visit 3 weeks or later following the last dose of study drug, the ETT Visit will replace the Safety Follow-up Visit (Section 9.1.2).

d The Day 1 Visit should be on the same day as the last scheduled visit of a parent study (Section 9.1.1). Subjects whose Day 1 Visit is NOT within 1 day of the last scheduled visit of a parent study will repeat all Day 1 assessments. Subjects whose Day 1 Visit is within 1 day of the last scheduled visit of a parent study will NOT have to repeat any Day 1 assessments that were specified to be performed at the last scheduled visit in a parent study. Subjects who resume participation in this study after discontinuation from another qualified Vertex study will complete the Returning Visit (which will consist of all assessments in the Day 1 Visit) and will resume treatment with ELX/TEZ/IVA after completion of the Returning Visit. Study visit numbering for returning subjects will resume based on the last study visit before the Departing Visit in this study. If the subject's Returning Visit window coincides with a scheduled study visit in this study, only the Returning Visit assessments will be completed, after which subjects will resume study visits in this study. Subjects who resume participation but have their first dose of study drug in this study delayed will repeat the safety assessments specified to be performed at the Returning Visit before receiving their first dose of study drug.

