| Study drug count                   | X                                                                        |                                                          | X                                   | X                          | X                                             | X                                                                                       |                                                                                                                                                                                                                                      |
| Study drug dosing                  | Day 1 through evening before Week 48 Visit                               |                                                          |                                     |                            |                                               |                                                                                         | Subjects on study drug interruption from a parent study or another qualified Vertex study may NOT begin dosing until they meet the resumption criteria in Section 9.8. Refer to Section 9.6.1 for study drug administration details. |
| Adverse events                     | Continuous from signing of ICF through completion of study participation |                                                          |                                     |                            |                                               |                                                                                         | Section 11.2.1                                                                                                                                                                                                                       |
| Medications review                 | Continuous from signing of ICF through completion of study participation |                                                          |                                     |                            |                                               |                                                                                         | Section 9.5                                                                                                                                                                                                                          |

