#### **ETT Visit**

If a subject prematurely discontinues study treatment for any reason other than to enroll in another qualified Vertex study, an ETT Visit should be scheduled as soon as possible after the subject decides to terminate study treatment.

If the ETT Visit occurs 3 weeks or later following the last dose of study drug, then the ETT Visit will replace the Safety Follow-up Visit, and a separate Safety Follow-up Visit will not be required.

If a subject withdraws consent for the study, no further assessments will be performed. Vertex may retain and continue using the study data and samples after the study ends, and may use the samples and information in the development of the study compound, for other drugs and diagnostics, in publications and presentations, and for education purposes. If a subject withdraws from the study, the study data and samples collected will remain part of the study (Section 9.9).

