### **9.1.5 Completion of Study Participation**

Completion of study participation for each individual subject is defined as: the Safety Follow-up Visit; or, in situations in which the ETT Visit, Departing Visit, or the Week 48 Visit replaces the Safety Follow-up Visit (Section 9.1.2), the ETT Visit, Departing Visit, or the Week 48 Visit.

If subjects withdraw consent or assent, completion of study participation is defined as date of withdrawal of consent or assent, whichever is earlier (Section 9.9).

If subjects are lost to follow-up (Section 9.1.4), the date of completion of study participation will be defined as the date of last contact.

The end of study is defined in Section 13.2.9.

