### **9.8 Study Drug Interruption and Stopping Rules**

In subjects who have interrupted study drug for >72 hours for any reason, the investigator should resume study drug only after a thorough investigation of the cause for interruption. The investigator will evaluate the subject's clinical stability and should consider resumption of study drug only after the subject is clinically stable and there is no comorbidity or condition that, in the opinion of the investigator, might confound the results of the study or pose an additional risk in administering study drug to the subject.

The medical monitor should be notified of an interruption of study drug that lasts >72 hours for any reason and of the resumption of study drug after such interruption. In subjects for whom study drug was previously interrupted, the medical monitor should be notified of any plan to discontinue study drug, before the discontinuation has occurred, if possible.

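### SAP Appendix A assigns an early-termination visit to Safety Follow-up by study day (>351), not by time since last dose, so values 21–28 days off drug can be reported as Week 12–48 results

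*SAP*

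**What the plan says.** **Protocol.** Section 9.1.2 provides that "For subjects who complete an ETT Visit/Departing Visit 3 weeks or later following the last dose of study drug", that visit takes the place of the Safety Follow-up Visit. Section 9.1.3 repeats this for the ETT alone: "If the ETT Visit occurs 3 weeks or later following the last dose of study drug". Neither section sets a condition on study day. Section 9.1.5 makes the ETT, Departing or Week 48 Visit the end of participation "in situations in which the ETT Visit, Departing Visit, or the Week 48 Visit replaces the Safety Follow-up Visit".

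**SAP.** Appendix A, Table 12-1, places weight/BMI, vital signs, hematology and chemistry in four windows (OL Weeks 12, 24, 36 and 48) and coagulation in two (Weeks 24 and 48). Within a window, "The measurement closest to the target day will be used", and ties go to the latest value. These assessments have no ETT row. The only rule that moves an ETT to follow-up is note 4, where the subject has no nominal Safety Follow-up visit and "has an ETT visit with study day >351, then the ETT visit will be mapped into Safety Follow-up analysis visit". ECG differs: it has its own nominal ETT/Departing row.

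**TE Period.** Protocol 12.3.1 excludes time spent in another qualified study. The definition in SAP 9.1 lacks that exclusion, although SAP 9.2.5 and 9.2.6 apply it to exposure and compliance.

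**The concern.** The two documents use different criteria for the same visit. The protocol looks at time off drug. The SAP looks at study day, with a cut-off suited to someone who has dosed for about 48 weeks, whereas ETT visits belong to people who stop earlier.

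A late ETT has a documented route. Study drug is interrupted; under protocol 9.8, "the investigator should resume study drug only after a thorough investigation of the cause for interruption"; and by Table 3-1 footnote b, "an ETT Visit should be scheduled as soon as possible after the decision to discontinue treatment". The ETT is thus timed from the decision, not from the last dose, and weeks may separate them.

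Laboratory values and vital signs are part of the primary endpoint and are summarized by visit. If such an ETT falls before Day 352, its off-drug value can appear under a Week label and be absent from the follow-up row.

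The TE Period omission is a separate matter. As written, an adverse event that began in the other study and is ongoing at the Returning Visit fits both the SAP's TEAE definition and its pre-treatment flag (SAP 9.3.1).

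**Working it through.** **1. Where 351 comes from.** Target days are 85, 169, 253 and 337 (Table 12-1). Midpoints: (85+169)/2 = 127; (169+253)/2 = 211; (253+337)/2 = 295. The last bound is (337+365)/2 = 351, with 365 = 337+28. The SAP figure is reproduced, and it presumes follow-up about 28 days after a full course.

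**2. Such an ETT is inside the by-visit summaries.** These cover the TE Period (SAP 9.3.2, 9.3.4), which ends 28 days after the last dose or at completion of participation, whichever is first (SAP 9.1). Here completion is the ETT itself (protocol 9.1.5). So the range to examine is d = 21 to 28 days off drug.

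**3. How often note 4 catches it.** Dosing runs "Day 1 through evening before Week 48 Visit", so with Week 48 on target the last-dose day L is 1 to 336, and ETT day = L + d. Note 4 needs L + d > 351: L ≥ 331 at d = 21, down to L ≥ 324 at d = 28. Counts for d = 21 to 28: 6+7+8+9+10+11+12+13 = 76, out of 336 × 8 = 2,688 (2.8%).

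**4. When the ETT becomes the reported Week value.** Assume scheduled visits are attended on target up to the ETT. If the ETT falls on or before its window's target day, every earlier value in that window is farther from target, so the ETT is used. If it falls later, the on-target visit is used. Unscheduled tests before the ETT change nothing. The qualifying ETT days are 22–85, 128–169, 212–253 and 296–337; for coagulation, 22–169 and 254–337.

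| | d = 21 | d = 28 |
|---|---|---|
| Four-window assessments | 64+42+42+42 = 190 of 336 (56.5%) | 57+42+42+42 = 183 of 336 (54.5%) |
| Coagulation | 148+84 = 232 of 336 (69.0%) | 141+84 = 225 of 336 (67.0%) |

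Pooled over d = 21 to 28, the four-window count is 1,492 of 2,688 (55.5%).

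**5. Worked case.** Last dose Day 130, ETT Day 153: 153 − 130 = 23 days off drug. Since 127 < 153 ≤ 169, it is reported as OL Week 24, and the subject has no follow-up value.

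**6. TE Period.** Appendix C classifies adverse events by comparing start date with the TE Period. Without the exclusion, an event starting in the other study lies inside that period. Likewise, Table 12-2 would class a medication taken only during the other study as concomitant, while SAP 9.2.4 treats new or changed medication in that interval as prior.

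**The case against.** The strongest reply is that the protocol sections govern attendance, not analysis. Section 9.1.2 also lets a Week 48 Visit replace follow-up for subjects who transition to other treatment, and a Week 48 value plainly belongs in the Week 48 row. Week labels are time windows, not claims of being on drug, and ETT values 1–20 days off drug stay in them anyway. This is right as far as it goes: the SAP breaks no protocol analysis rule. But Day 21 is not arbitrary. Follow-up is due 28 ± 7 days after the last dose, so 28 − 7 = 21 is its earliest day. The same measurement goes to the follow-up row if the visit is labelled Safety Follow-up and to a Week row if it is labelled ETT.

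Second, the fix is partial. In 676 of the 2,688 combinations (25%), the target day falls between last dose and ETT, and the Week value is a scheduled visit already 1–27 days off drug. The count is the sum over d of 3(d−1)+14, that is 3 × 188 + 8 × 14. An ETT on Day 352 after a last dose on Day 336 (16 days off) would still go to follow-up. Both stand; the proposal does not claim to make Week rows on-drug only.

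Third, a missing last-dose date in a subject who discontinued is imputed first from the ETT date, giving 0 days off drug. That visit would simply be handled as it is now.

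Fourth, few subjects are affected. That stands and sets the severity. Late Departing Visits should be rarer still, since that visit is tied to the start of the other study's Run-in.

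On the TE Period, the pre-treatment flag is the more specific rule and probably prevails for events ongoing at return. It does not settle the Appendix C comparison or the medication table.

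**Conclusion.** The concern holds and is minor. Note 4 catches 2.8% of the combinations in which an ETT is 21–28 days off drug. With scheduled visits on target, the off-drug ETT is the reported Week value for 54.5–56.5% of possible last-dose days (67.0–69.0% for coagulation). These are shares of an even grid of days, not of subjects. The documents give neither a discontinuation rate nor ETT timing, so the number of late ETTs cannot be computed; it should be small because ETTs are due promptly.

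Each case moves one value per parameter in rows of at most about 160 subjects. The effect of note 4 is confined to descriptive by-visit summaries: TEAE and threshold counts use the whole TE Period, individual values are still listed, and ECG is unaffected. The TE Period omission is a separate drafting gap that also holds.

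**What to change.** Add to note 4: *where there is no nominal Safety Follow-up visit, an ETT or Departing Visit 21 or more days after the last dose in this study is mapped to Safety Follow-up whatever its study day, and is not used in any Week window; ECG keeps its nominal rows.* Retain the existing Day 351 sentence for other ETT visits, so that none is left without an analysis visit.

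In SAP 9.1, add to the TE Period definition the sentence from protocol 12.3.1 that excludes time in another qualified study for subjects who return.

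The cost is two SAP sentences and a one-line programming condition on days since last dose. No new data and no protocol change are needed.
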